1. Title

Effectiveness of 'Behavioural Change Communication Model' in Promoting Physical Activity Among Females with Type 2 Diabetes Mellitus: A Randomized Controlled Trial.

2. Introduction

Rationale of the Study: The global prevalence of Type 2 Diabetes Mellitus (T2DM) is rising rapidly, far surpassing previous predictions. A central pathological feature of T2DM is **insulin resistance**, which is significantly driven by **physical inactivity**. While physical activity (PA) is a low-cost, effective non-pharmacological intervention, it remains underutilised, particularly among females in certain social contexts. In South India, females are highly affected by diabetes and often follow sedentary lifestyles. This study addresses the need for tailored behavioural change strategies to promote a context-specific physical activity culture.

3. Review of Literature

- **Global Burden:** The number of people with diabetes was projected to reach 300 million by 2025 but already hit 537 million by 2021.
- **Role of PA:** Exercise improves glucose tolerance, upregulates insulin receptors, and reduces insulin resistance.
- **Behavioural Change:** The **Transtheoretical Model (TTM)** provides a framework for behaviour change through five stages: pre-contemplation, contemplation, preparation, action, and maintenance.
- **Interventions:** Stage-matched materials and motivational readiness assessments can create cost-effective interventions for individuals prepared to initiate change.

4. Materials & Methods (Methodology)

- **Research Question:** Will a "behavioural change communication model" implemented in a Diabetic Clinic OP among females with Type 2 DM be effective in making them more physically active?.
- **Aim:** To evaluate the effectiveness of a BCC model in promoting physical activity among female T2DM patients.
- **Objectives:**
 - **Primary:** To measure the increase in physical activity in Metabolic Equivalent Task (MET) scores using a PA questionnaire.
 - **Secondary:** To assess changes in **HbA1C** levels, knowledge of diabetes and PA, and the stage of behaviour change.
- **Hypothesis:** A standardized BCC model will improve physical activity, knowledge, and the stage of behaviour change in the intervention group compared to a control group receiving only pamphlets.
- **Study Design:** Randomized controlled trial (RCT).
- **Setting:** Diabetic Clinic outpatient department at a government tertiary care hospital in South India.
- **Sampling:**
 - **Sample Size:** 86 females (43 in the intervention group, 43 in the control group).
 - **Inclusion Criteria:** Females with Type 2 DM aged 30–65 years.

- **Exclusion Criteria:** Patients with complications (nephropathy, H/O myocardial infarction), those advised against exertion, and multiple patients from the same family.
- **Sampling Procedure:** Consecutive recruitment followed by **block randomization** using RALLOC software.
- **Methods:**
 - **Data Collection:** Trained assistants use an interview schedule to collect demographic, clinical, and PA data (IPAQ-long form).
 - **Intervention:** The **BCC model** includes a 30-minute PA promotion video, pamphlets, and recall/report of PA over four monthly visits.
 - **Outcome Measurement:** Total and specific PA under four domains (occupational, domestic, transportation, leisure) measured in MET scores and converted to calories/day.

5. Plan of Analysis

- **Statistical Software:** SPSS.
- **Analysis Methods:**
- Data distribution will be analysed. If normal distribution, parametric methods will be used. If skewed distribution, normalisation of data and non-parametric methods will be considered.
 - Baseline physical activity difference will be adjusted for comparing the control and intervention groups.
- **Sample Size Calculation:** Based on a 95% CI and a pooled standard deviation (18) from a pilot study of 15 subjects

- **sample size calculation**

Estimating the difference between two means
SD from pilot study-18

$$n = z^* - a / 2(2sp^*) / d^*$$

- 2-tailed
- Precision-10)
- Desired CI-95%
- no. in one arm=39
- Expecting 5% drop outs
- $39 / (1 - .05)^2 = 43$

Sampling Method

Consecutive sampling from Diabetic clinic OP for 5 consecutive Fridays based on screening questionnaire with inclusion and exclusion criteria

6. Policy Implications

The study highlights that motivation and reinforcement are effective strategies for fostering self-management responsibilities in T2DM patients. Implementing such behavioural models in clinical settings can help bridge the gap between patient awareness and actual lifestyle changes.

7. References

References should be formatted in **Vancouver style**.

8. Annexures

- **Instrument of Measurement:** International Physical Activity Questionnaire (IPAQ) short form
- **Knowledge & SOC Questionnaires:** 7-question knowledge set and Stage of Change (SOC) assessment.
- **Ethical Clearance:** Obtained on 17/05/2006.
- **Consent Forms:** Provided in English and local languages.

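### The stated sample size inputs (SD 18, precision 10, two-sided 95% CI) give 25 per arm, not 39; at least one of the three figures is misstated

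*Protocol*

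**What the plan says.** The calculation is in section 5 of the protocol (Plan of Analysis), under the sample size heading. The method is named as "Estimating the difference between two means". The inputs are "SD from pilot study-18", described just above as a "pooled standard deviation (18) from a pilot study of 15 subjects"; a two-tailed setting; a precision of 10; and a desired confidence level of 95%. No power is given, and neither the SD nor the precision has a unit.

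The result is "no. in one arm=39". The next line is "Expecting 5% drop outs", and 39 is divided by the square of 0.95 to give 43. Section 4 (Materials & Methods, Sampling) carries this forward as the enrolment target: "86 females (43 in the intervention group, 43 in the control group".

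**The concern.** The protocol gives every input that a precision-based calculation needs, and it gives the result, so the result can be checked in one line. It does not follow from the inputs. This is the only justification offered for the sample size, and the target of 86 rests on it.

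Two things are at stake. First, a published report that repeats these figures will state a precision, an SD or a sample size that is wrong, and any reader can find this. Second, which figure is wrong affects what the trial can show. If the SD is right, the interval will be tighter than stated. If the SD really used was larger, the trial is less informative than an SD of 18 suggests.

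**Working it through.** **Inputs, all from section 5 of the protocol:** SD s = 18; precision d = 10, read as the half-width of the confidence interval; two-sided 95%, so z = 1.96; stated n = 39 per arm.

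**Formula.** The exponents of the printed formula are lost in the text at hand, but its terms (z at α/2, 2sp, d) and the named method match the standard one: n per arm = z² × 2s² / d².

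**Stated inputs.** 3.8416 × 2 × 324 / 100 = 24.9, so 25 per arm. The stated 39 is not reproduced: 39 / 25 = 1.56.

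**Could another reading give 39?** With SD 18 and d = 10 kept:

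| Reading | n per arm |
|---|---|
| t quantiles in place of z | 27 |
| One-sided 95% | 18 |
| 99% confidence | 43 |
| 10 as the full width (d = 5) | 100 |
| (z × 2s / d)² | 50 |
| Formula with squares left out, three ways | 8, 13 or 14 |
| Width met with 80% to 99% assurance | 30 to 37 |

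None gives 39. Adding a power term that the protocol does not state, for a difference of 10, gives 40 (two-sided, 70% power), 41 (one-sided, 80%) or 51 (two-sided, 80%). These do not give 39 either, and the one-sided version contradicts the two-tailed setting.

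**What would give 39?** The formula depends only on the ratio s/d. Solving for n = 39: s/d = √(39/2) / 1.96 = 2.25. Two examples:
- s = 18 with d = 8: 3.8416 × 648 / 64 = 38.9, so 39.
- d = 10 with s = 22.5: 3.8416 × 2 × 506.25 / 100 = 38.9, so 39.

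Neither 8 nor 22.5 appears in the protocol, and any other pair with a ratio near 2.25 would serve as well.

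**What the sample delivers if SD 18 is right.** Half-width = 1.96 × 18 × √(2/n):
- n = 39: 7.99
- n = 41 (43 × 0.95 = 40.85): 7.79
- n = 43: 7.61

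**Detectable difference, for context.** For an unadjusted two-sample t-test with SD 18, two-sided 5% level and 41 per arm, the difference detectable with 80% power is 11.3, and power for a difference of 10 is 70%. The protocol plans to adjust for baseline physical activity. If 18 is an unadjusted SD, adjustment multiplies it by about √(1 − r²), where r is the baseline-outcome correlation. The protocol gives no r, so this range is an assumption:

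| r | 80%-power difference | Power for 10 |
|---|---|---|
| 0 | 11.3 | 70% |
| 0.3 | 10.8 | 74% |
| 0.5 | 9.8 | 82% |
| 0.7 | 8.1 | 94% |

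**The case against.** The strongest reply is that the mismatch does no harm. If SD 18 is right, 39 per arm more than meets a precision of 10, nobody extra needs recruiting, and no conclusion changes. This stands, and it is why the point is a correction of wording and not a threat to the trial.

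The text around the calculation is also damaged: the formula has lost its exponents, and the precision line ends in an unmatched bracket, so characters may be missing next to a disputed number. This limits what can be said about the cause. It does not rescue the arithmetic, because the figures printed are legible, the SD of 18 appears twice, and no reading of the formula that was tried gives 39.

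Two stronger readings are tempting, and the protocol supports neither.

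- *That the precision is the wrong figure and should have been 8.* It is the simplest explanation, since 18 and 8 give exactly 39 after rounding up. But 8 is back-calculated and stands nowhere in the protocol; a different SD or an unstated input would do equally well.
- *That the trial lacks power for a difference of 10.* The protocol never calls 10 a detectable difference. It describes estimation with a desired precision, and sizing on interval width is a legitimate choice even with a comparative hypothesis. The 70% power applies only to an unadjusted comparison; with the planned baseline adjustment and an assumed correlation of 0.5 it would be 82%.

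**Conclusion.** The sample size statement contradicts itself. SD 18, precision 10 and a two-sided 95% interval give 25 per arm; the protocol says 39. At least one of the three figures is misstated, and the document does not show which. That conclusion rests on the standard formula for a difference between two means, with precision read as the half-width, and the alternatives tried do not change it.

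The consequence is limited. If SD 18 is right, the error is in the safe direction: the half-width is about 8.0 at 39 per arm, against the 10 claimed. If precision 10 and n = 39 are right, the SD used was about 22.5, and the stated 18 understates the variability the trial was planned for. Neither case calls for a change in the enrolment target. This should be fixed, because the target's only stated basis cannot be reproduced, but it is not critical.

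**What to change.** Keep 43 per arm; do not cut the sample to 25. Retrieve the original calculation and restate SD, precision and n so that they agree. Give the unit of the SD and of the precision, since the outcome is described both as MET scores and as calories per day.

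- If SD 18 is confirmed, state the precision delivered: a 95% CI half-width of about 8.0 at 39 per arm, or 7.8 with about 41 evaluable per arm.
- If precision 10 and n = 39 are confirmed, state the SD used (about 22.5) and where it came from.

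A line on detectable difference is optional. If one is added, label it as an unadjusted comparison with SD 18 (about 11.3 at 80% power with 41 per arm), and say that baseline adjustment would lower it by an amount that depends on a correlation not yet specified.

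While the paragraph is open, the dropout step can be tidied. Dividing by the square of 0.95 gives 43.2, shown as 43; the usual 39 / 0.95 = 41.05 gives 42. This is a separate, small matter and does not explain the gap between 25 and 39.

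The cost is a few lines of text, with no extra patients and no change to recruitment.
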